11.2 Analysis of Adverse Events

All adverse events will be coded using the most current version of the Medical Dictionary for Regulatory Activities (MedDRA). A treatment-emergent adverse event (TEAE) is defined as any adverse event that begins or worsens in severity on or after the first study drug dose date and no more than 20 weeks after the last study drug dose date. Analysis of adverse events will also be conducted by geographical region (North America including US and Canada, European countries plus Australia, and Japan).

11.2.1 Adverse Event Overview

The number and percentage of subjects experiencing one or more adverse events in the following adverse event categories will be summarized for each treatment group, ABBV-8E12 Overall. No comparisons of treatment groups will be performed.

- Any TEAE
- Any TEAE that was rated as having reasonable possibility of being related to study drug by the investigator
- Any severe TEAE
- Any serious TEAE
- Any TEAE that led to discontinuation of study drug
- Any fatal TEAE
- All deaths

11.2.2 Adverse Event Incidence

TEAE incidence will be summarized and presented using primary MedDRA system organ classes (SOCs) and preferred terms (PTs). The system organ classes will be presented in alphabetical order and the preferred terms will be presented in alphabetical order within each system organ class. Subjects reporting more than one adverse event for a given MedDRA PT will be counted only once for that term. Subjects reporting more than one adverse event within a SOC will be counted only once for the SOC total. Subjects reporting more than one adverse event will be counted only once in the overall adverse event total.

The number and percentage of subjects experiencing one or more TEAEs will be summarized by PT for each treatment group, ABBV-8E12 Overall. The PTs will be presented by decreasing frequency in ABBV-8E12 Overall.

The number and percentage of subjects experiencing one or more adverse events in the following adverse event categories will be summarized by primary SOC and PT for each treatment group, ABBV-8E12 Overall.

- Any TEAE
- Any serious TEAE
- Any TEAE that led to discontinuation of study drug

- Any TEAE assessed by the investigator to have Reasonable Possibility of Being Related to study drug

The number of subjects experiencing one or more TEAEs will also be summarized by maximum severity category (mild, moderate, severe and unknown) and primary SOC and PT for each treatment group, ABBV-8E12 Overall. Subjects reporting more than one TEAE for a given PT will be counted only once for that term in the most severe category reported. If a subject has an adverse event with unknown severity, then the subject will be counted in the severity category of "unknown" even if the subject has another occurrence of the same event with a severity present. The only exception is if the subject has another occurrence of the same adverse event with the most extreme severity – "Severe." In this case, the subject will be counted under the "Severe" category. No comparisons of treatment groups will be performed.

The number of subjects experiencing one or more TEAEs will also be summarized by maximum relationship category (Reasonable Possibility of Being Related, No Reasonable Possibility of Being Related and Unknown), as assessed by the investigator, and primary SOC and PT for each treatment group, ABBV-8E12 Overall. Subjects reporting more than one TEAE for a given PT will be counted only once for that term in the most related category reported. If a subject has an adverse event with unknown relationship, then the subject will be counted in the relationship category of "unknown," even if the subject has another occurrence of the same event with a relationship present. The only exception is that if a subject has another occurrence of the same adverse event with a relationship assessment of "Reasonable Possibility of Being Related." In this case, the subject will be counted under the "Reasonable Possibility of Being Related." No comparisons between treatment groups will be performed.

11.2.3 Listing of Adverse Events

The following additional summaries of adverse events will be prepared.

- List of subject numbers associated with each PT for all TEAEs

- List of subject numbers associated with each PT for all TEAEs assessed by the investigator as having Reasonable Possibility of Being Related.
- Listing of all serious adverse events
- Listing of all adverse events that led to discontinuation of study drug
- Listing of all fatal adverse events
- Listing of all deaths

11.3 Analysis of Laboratory Tests

The laboratory tests are described in the following table.

Hematology	Clinical Chemistry	Urinalysis
Hematocrit	Blood urea nitrogen (BUN)	Specific gravity
Hemoglobin	Creatinine	pH
Red blood cell (RBC) count	Total bilirubin	
White blood cell (WBC) count	Albumin	
Neutrophils	Aspartate aminotransferase (AST)	
Bands (if detected)	Alanine aminotransferase (ALT)	
Lymphocytes	Alkaline phosphatase	
Monocytes	Sodium	
Basophils (if detected)	Potassium	
Eosinophils (if detected)	Calcium	
Platelet count (estimate not acceptable)	Inorganic phosphate	
Mean corpuscular volume (MCV)	Uric acid	
Mean corpuscular hemoglobin concentration (MCHC)	Cholesterol	
Prothrombin time (PT)	Total protein	
Activated partial thromboplastin time (aPTT)	Glucose	
PT/INR (Prothrombin Time/International Normalized Ratio)	Triglycerides	
	Bicarbonate/Carbon Dioxide (CO ₂) Chloride	

11.3.1 Analysis of Mean Changes for Laboratory Tests

Analyses of mean change from baseline to each double-blind visit value and to the minimum, maximum and final double-blind value will be presented for each continuous

hematology, chemistry and urinalysis variable. Analyses of mean change from final double-blind value to final post-treatment value will also be presented for each continuous hematology, chemistry, urinalysis, and vital sign variables.

For each mean change analysis, the mean and median change will be presented for each treatment group. The mean change for each ABBV-8E12 dose group will also be compared to the mean change for the placebo group using an ANOVA with treatment as the factor. *P* values and 95% confidence intervals will be calculated based on pairwise contrasts within the ANOVA.

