For all laboratory abnormalities the investigator will determine if they indicate a new disease process, an exacerbation or worsening of an existing condition, or require further action to be taken and therefore need to be reported as adverse events. Accordingly, for any values outside of the reference range, the Investigator will indicate on the report if the result is Clinically Significant (CS) or Not Clinically Significant (NCS). If a laboratory abnormality meets criteria for a Potentially Clinically Significant (PCS) laboratory value, as defined in [Appendix D](#), the investigator must either report an associated adverse event or document in source the reason(s) the finding was not considered an adverse event.

Any laboratory value that remains abnormal at Premature Discontinuation/End of Study and was judged to be clinically significant will be followed according to accepted medical standards until resolution of the abnormality.

Magnetic Resonance Imaging (MRI)

For all subjects, a Magnetic Resonance Imaging (MRI) of the brain will be obtained at time points indicated in the Study Activities Table ([Appendix C](#)) and interpreted by a radiologist or neurologist. The subjects will be positioned supine on the MRI bed and their head will be positioned within a head coil with appropriate foam padding to decrease movement during the scan and to standardize the orientation of the head. The subjects will then be positioned within the MRI scanner for imaging. The screening MRI should

be completed after all other relevant screening procedures (except LP) have been completed and reviewed by the investigator.

The screening MRI assessment will be used to rule out the presence of any intracranial masses that might preclude the subject from undergoing a lumbar puncture, and exclude focal or diffuse processes that could indicate a clinically significant neurologic disorder other than PSP, including signal abnormalities on fluid attenuated inversion recovery (FLAIR) or T2 weighted images consistent with infectious, vascular, neoplastic or other degenerative processes. The 3D T1 weighted sequences will also be acquired for volumetric analysis that will enable a quantitative assessment of whole brain volume and regional brain volume.

All or a subset of the following brain MRI imaging sequence types will be performed:

- T1 weighted
- Diffusion weighted imaging
- T2 weighted FLAIR
- PD/T2 weighted
- T2* weighted
- Diffusion tensor imaging

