	Week 24	Week 28	Week 32	Week 36	Week 40	Week 44	Week 48	Completion/ Premature Discontinuation	Post- Treatment Follow-Up	Post- Treatment Follow-Up	Post- Treatment Follow-Up		
Activities ^c	Day 169	Day 197	Day 225	Day 253	Day 281	Day 309	Day 337						
Physical Examination ^f	X							X					
Orthostatic Vital Signs ^g	X	X	X	X	X	X	X	X	X	X	X	X	X
Body Weight	X	X	X	X	X	X	X	X	X	X	X	X	X
Pregnancy Test (Females only) Urine (u) Serum (s) ⁱ	U						U	S					
Neurological Exam	X			X				X			X		
12-Lead ECG ^j	X			X				X			X		
Clinical Laboratory Tests	X							X					
Administer IV Study Drug	X	X	X	X	X	X	X						
Brain MRI ^{k,l}	X							X					
Lumbar Puncture (LP)/CSF Collection ^{m,n}								X					
Serum Plasma Biomarkers		X						X					
Optional Exploratory Pharmacogenetic DNA and RNA Sample ^o				X				X					
Blood PK Levels	X			X				X			X		X
Serum Antibodies (ADA)	X			X				X			X		X
PSP Rating Scale (PSPRS)	1			1				1					
CGI-S	2		5	2			5	2					

Weeks of Study Drug Exposure	Treatment Period ^b																
	Dose 8	Dose 9	Dose 10	Dose 11	Dose 12	Dose 13	Dose 14	Week 52	Week 60	Week 68							
	Week 24	Week 28	Week 32	Week 36	Week 40	Week 44	Week 48	Completion/ Premature Discontinuation	Post- Treatment Follow-Up	Post Treatment Follow-Up							
Day 169	Day 197	Day 225	Day 253	Day 281	Day 309	Day 337											
Activities ^c																	
CGI-C	3		6	3			6	3									
SEADL	4			4				4									
UPDRS Part II	5			5				5									
RBANS			1				1										
Color Trails Test (CTT) Parts 1 & 2			2				2										
Letter Fluency Test (LFT)			3				3										
NNIPPS-PPS [#]			4				4										
PGI-C ^r	X			X									X				
PSP-QoL ^r	X			X									X				
Euro-QoL-5D (EQ-5D) ^r			X									X					
C-SSRS ^r	X	X	X	X	X	X	X	X	X	X	X	X	X	X	X	X	X
Concomitant Medication	X	X	X	X	X	X	X	X	X	X	X	X	X	X	X	X	X
Adverse Event Assessment ^s	X	X	X	X	X	X	X	X	X	X	X	X	X	X	X	X	X
24-hour confinement ^t																	
Telephone Contact ^v	X			X									X				

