- Week 52 Rx Days > 350

For measurements that are planned to be collected during double-blind treatment period at Weeks 2, 4, 8, 12, 24, 48, and 52, i.e., clinical laboratory tests will be mapped to an analysis "week" according to the following windows defined by Rx day.

- Week 2 Rx Day 2 through 21 (Cohort J1 only)
- Week 4 Rx Day 22 through 42 (Cohort J1 only)
Rx Day 2 through 42 (Cohort 1 only)
- Week 8 Rx Day 43 through 70 (Cohort 1 and Cohort J1 only)
- Week 12 Rx Days 71 through 126 (Cohort 1 and Cohort J1 subjects)
Rx Days 2 through 126 (Cohort 2 subjects)

- Week 24 Rx Days 127 through 252
- Week 48 Rx Days 253 through 350
- Week 52 Rx Days > 350

For measurements that are planned to be collected during double-blind treatment period at Weeks 1, 2, 4, 8, 12, 24, 36 and 52, i.e., ECG observations will be mapped to an analysis "week" according to the following windows defined by Rx day.

- Week 1 Rx Days 2 through 10 (Cohort 1 and Cohort J1 only)
- Week 2 Rx Days 11 through 21 (Cohort 1 and Cohort J1 only)
- Week 4 Rx Days 22 through 42 (Cohort 1 and Cohort J1 subjects)
Rx Days 2 through 42 (Cohort 2 subjects)
- Week 8 Rx Days 43 through 70
- Week 12 Rx Days 71 through 126
- Week 24 Rx Days 127 through 210
- Week 36 Rx Days 211 through 308
- Week 52 Rx Days > 308

For measurements that are planned to be collected during double-blind treatment period at Weeks 2, 12, 24, and 52, i.e., brain volumetric MRI observations will be mapped to an analysis "week" according to the following windows defined by Rx day.

- Week 2 Rx Days 2 through 49 (Cohort 1 and Cohort J1 only)
- Week 12 Rx Days 50 through 126 (Cohort 1 and Cohort J1 subjects)
Rx Days 2 through 126 (Cohort 2 subjects)
- Week 24 Rx Days 127 through 266
- Week 52 Rx Days > 266

For vital sign measurements and C-SSRS assessments that are planned to be collected during post-treatment follow-up period on Weeks 60 and 68, observations will be mapped to an analysis "week" according to the following windows defined by RxEnd day.

- Post-Treatment Week 12 RxEnd Days 46 through 112
- Post-Treatment Week 20 RxEnd Days > 112

For ECG measurements that are planned to be collected during post-treatment follow-up period at Weeks 60, observations will be mapped to an analysis "week" according to the following windows defined by RxEnd day.

- Post-Treatment Week 12 RxEnd Days > 45

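### The SAP tests laboratory change at Week 48 and after treatment, but the protocol schedules no laboratory test at Week 48 or in follow-up

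*SAP*

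**What the plan says.** **SAP 6.2 (Visit Definitions)** gives the double-blind laboratory visits as "Weeks 2, 4, 8, 12, 24, 48, and 52, i.e., clinical laboratory tests will be mapped". One of the windows that follow is "Week 48 Rx Days 253 through 350". Its post-treatment windows cover vital signs and C-SSRS (Weeks 60 and 68) and ECG (Week 60). There is none for laboratory tests.

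**SAP 11.3.1** plans two kinds of laboratory comparison that matter here:
- By visit: "Analyses of mean change from baseline to each double-blind visit value and to the minimum, maximum and final double-blind value will be presented".
- After treatment: "Analyses of mean change from final double-blind value to final post-treatment value will also be presented for each continuous hematology, chemistry, urinalysis". The same sentence also covers vital signs.

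For each of these, "The mean change for each ABBV-8E12 dose group will also be compared to the mean change for the placebo group using an ANOVA"; P values and 95% confidence intervals are to be given. SAP 11.1 defines post-treatment as more than 45 days and up to 20 weeks after the last dose.

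**Protocol Appendix C**, in the part of the schedule from Week 24 on, marks clinical laboratory tests at Week 24 and at Week 52/Premature Discontinuation only.

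**Protocol 8.1.6.2** tests arm differences only for change to the minimum, maximum and final laboratory value. It plans no visit-by-visit test and no post-treatment laboratory comparison. SAP 14.0 does not list either as a change from the protocol.

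**The concern.** A comparison of arms at a visit is a comparison of the randomised groups only if the visit was planned for everyone. If no such visit exists, whoever has a value in the window is there for a reason: the subject stopped early, had a result repeated, was seen for a clinical problem, or was off the dosing schedule. Protocol 5.3.1.1 names one such route after treatment: "Any laboratory value that remains abnormal at Premature Discontinuation/End of Study and was judged to be clinically significant will be followed" until it resolves.

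The tables would nevertheless carry P values and confidence intervals in the same format as the real visits, and a reader would take them as randomised evidence about laboratory change late in treatment or off drug. The Week 48 window also pulls genuine discontinuation results out of the adjacent Week 24 and Week 52 windows and reports them under a visit that the schedule does not contain.

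**Working it through.** **1. Reading the schedule.** The columns of Appendix C can be placed from rows whose timing is known. Infusions fill the first seven columns (Weeks 24 to 48). Pregnancy tests fall at Weeks 24, 48 and 52. The ECG and PK rows match the visits written out in Protocol 5.3.1.1 and 5.3.2.1, including Week 60 (ECG) and Weeks 60 and 68 (PK). The laboratory row has marks in the first and eighth columns: Week 24 and Week 52. Brain MRI has the same two.

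**2. Reproducing the SAP's windows.** Nominal days are Week 12 = 85, Week 24 = 169, Week 48 = 337 and Week 52 = 337 + 28 = 365. Each boundary is the midpoint of neighbouring visits:
- (85 + 169)/2 = 127
- (169 + 337)/2 = 253
- (337 + 365)/2 = 351

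This gives Week 24 = 127–252, Week 48 = 253–350 and Week 52 > 350, exactly as SAP 6.2 states. The windows were built as if a Week 48 laboratory visit existed.

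**3. Windows that match the schedule.** With visits at Weeks 12, 24 and 52, the second boundary is (169 + 365)/2 = 267. So Week 24 = 127–266 and Week 52 > 266. These are the SAP's own MRI windows. The Week 48 window thus takes 14 days (253–266) from Week 24 and 84 days (267–350) from Week 52, 98 days in all.

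**4. A subject on schedule.**
- The Week 52 visit, ±4 days, falls on Rx Days 361–369, after Day 350, so it is not in the Week 48 window.
- It is 361 − 337 = 24 to 369 − 337 = 32 days after dose 14. If that dose also moved by ±4 days, the range is 361 − 341 = 20 to 369 − 333 = 36. Both are below 45, so the value is double-blind.
- No later visit has laboratory tests.

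The planned number of laboratory values is therefore 0 at Week 48 and 0 after treatment.

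**5. Who can contribute.**
- Subjects who discontinue: Protocol 5.4.1 requires laboratory tests at that point, whenever it falls.
- Repeats and follow-up of clinically significant abnormal values (Protocol 5.3.1.1).
- Unscheduled visits for any clinical indication (Appendix C notes).
- Possibly the CBC and coagulation results required before a lumbar puncture. Their timing is not stated, so whether they reach either period is an assumption.
- Completers who missed dose 14. Their last dose is on Day 309, so Week 52 is 361 − 309 = 52 to 369 − 309 = 60 days later (48 to 64 if that dose also moved by ±4 days). Above 45 days, the SAP classes those scheduled Week 52 results as post-treatment. Such a subject has 13/14 = 92.9% of doses and still meets the protocol's 90% compliance threshold. With no unscheduled test, the last double-blind laboratory value is from Week 24, so the post-treatment change spans about 365 − 169 = 196 days, most of it on drug.

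**The case against.** **A reader might infer that these results come only from discontinuers and subjects re-tested for abnormal values, and that no scheduled test contributes.** The documents do not support that. Unscheduled visits, possibly pre-puncture blood draws, and completers who missed dose 14 can also contribute, the last through a scheduled Week 52 test. These additional sources are still unplanned for the time point or off the dosing schedule, so the comparison remains non-randomised.

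**A reader might infer a false reversible drug effect through regression to the mean.** That needs selection that differs between arms. If blinded investigators repeat abnormal values alike in all arms, recovery appears in all of them and produces no difference by itself. The documents give no evidence either way, so the objection stands: the direction of any bias is unknown.

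**The schedule evidence is one table.** This is fair in part. Protocol 5.3.1.1 allows more than the tabulated samples, and the columns of the SAP's own copy (SAP Table 2) cannot be read reliably, so it neither supports nor contradicts the point. The reading rests on Protocol Appendix C and on the absence of any post-treatment laboratory window in SAP 6.2.

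**Little depends on these rows.** This also stands. The minimum, maximum and final-value analyses, the shift tables and the PCS summaries do not use the Week 48 window, and nothing reaches efficacy or the error-rate control. Discontinuation results also enter other windows, but there they sit beside planned values.

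**Conclusion.** The point holds as a minor one. SAP 6.2 and 11.3.1 plan between-arm laboratory tests at Week 48 and after treatment that the protocol's schedule does not supply with data. Subjects on schedule contribute nothing to either, so the P values would describe a non-randomised subset. The 98-day Week 48 window also relabels real discontinuation results. How many subjects would contribute cannot be derived from the documents.

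The conclusion assumes that the Appendix C columns are as read above and that the SAP's 45-day rule governs. Protocol 8.1.6 instead separates the periods at 20 weeks after the last dose. Under that rule the completer who missed dose 14 stays in the double-blind period, and the post-treatment comparison still has no scheduled laboratory test to draw on.

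**What to change.** - **SAP 11.3.1:** remove laboratory variables from the analysis of change from final double-blind to post-treatment value, leaving it for vital signs and ECG (also covered in SAP 11.4.1 and 11.5.1). List post-treatment laboratory values by subject, without tests.
- **SAP 6.2:** delete Week 48 from the laboratory visits and use contiguous windows: Week 24 = Rx Days 127–266 and Week 52 > 266. Keep values from Rx Days 253–350 in the minimum, maximum, final and PCS summaries.
- **If Week 48 or follow-up laboratory tests were intended:** reconcile Protocol Appendix C, SAP Table 2 and SAP 6.2 instead, and record the added analyses in SAP 14.0.

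The cost is SAP wording and fewer tables. No data are lost. The small downside is that late discontinuation results are pooled into Week 52, as already happens for MRI.

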8.1.6 Safety Analyses

All safety analyses will be performed on the safety data set unless otherwise specified. Comparisons between each ABBV-8E12 dose group and placebo will be performed with two-sided test at the significance level of 0.050, if applicable. All safety assessments that are taken no more than 20 weeks after the last dose of study drug administration will be included in the safety evaluation of the Double-blind Treatment Period, and all safety assessments that are taken more than 20 weeks after the last dose of study drug will be included in the safety evaluation for the Post-treatment Follow-up Period.

Study Drug Exposure and Compliance

The number of doses on study drug will be summarized by treatment group and all treatment groups combined. The number and percentage of subjects with at least 90% compliance with study drug dosing will be summarized by treatment group and all treatment groups combined.

Adverse Events

A treatment-emergent adverse event (TEAE) is defined as any adverse event that begins or worsens in severity on or after the first study drug dose date and no more than 20 weeks after the last study drug dose date.

All other safety assessments that are taken no more than 20 weeks after the last dose of study drug will be included in the safety evaluation of the Double-blind Treatment Period, and all safety assessments that are taken more than 20 weeks after the last dose of study drug will be included in the safety evaluation for the Post-treatment Follow-up Period.

Unless otherwise specified, treatment group differences in continuous safety variables (e.g., change from baseline to final observation on laboratory tests) will be assessed using an ANOVA model with treatment as the main effect, and the treatment group differences in binary safety variables will be evaluated using Fisher's exact test.

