6.2 Visit Definitions

Definition of Rx Day (Days Relative to the First Dose of Study Drug)

Rx Day is calculated for each time point as the number of days between the day of the first dose of study drug and the specific time point. For dates before the first dose date of study drug, Rx day = date of time point – first dose date; for dates on or after the first dose date of study drug, Rx day = date of time point – first dose date + 1. Thus, Rx Day is a negative value when the time point of interest is prior to the first study drug dose day; Rx Day is a positive value when the time point of interest is on or after the first study drug dose day. There is no Rx Day 0. With this defined algorithm, the day of the first dose of study drug will be Rx Day 1.

RxEnd Day is calculated for each post-treatment time point as the number of days between the day of the last dose of study drug and the specific time point:
RxEnd Day = date of time point – last dose date. With this defined algorithm, the day of the last dose of study drug will be RxEnd Day 0.

Definition of Baseline and Final Observation

Unless otherwise specified, for all efficacy analyses and for all safety analyses of the double-blind Treatment Period, "baseline" shall refer to the last non-missing observation prior to the first dose of study drug and "final" for the double-blind Treatment Period shall refer to the last non-missing observation no more than 45 days after the last dose of the study drug for both efficacy variables and safety variables. The "final" for the post-treatment follow-up period for safety variables shall refer to the last non-missing observation greater than 45 days but no more than 20 weeks after the last dose of study drug.

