11.0 Safety Analysis

11.1 General Considerations

All safety analyses will be performed on the safety dataset. Treatment group differences in safety parameters are evaluated using two-sided test at the significance level of 0.050. When statistical tests are performed, the comparisons will be between each ABBV-8E12 dose and placebo. With the exception of adverse events, all safety assessments that are taken no more than 45 days after the last dose of study drug will be included in the safety evaluation of the Double-blind Treatment Period. All safety assessments that are taken more than 45 days but no more than 20 weeks after the last dose of study drug will be included in the safety evaluation for the Post-Treatment Follow-Up Period.

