11.4.1 Vital Sign and Weight Mean Changes

Diastolic blood pressure, systolic blood pressure and pulse will be analyzed separately for each position of measurement. Analyses of mean change from baseline to each double-blind visit value and to the minimum, maximum and final double-blind value will be presented for each vital sign and weight variable. Analyses of mean change from final double-blind value to each post-treatment visit will also be presented for vital sign variable.

For each mean change analysis, the mean and median change will be presented for each treatment group. The mean change for each ABBV-8E12 dose group will also be compared to the mean change for the placebo group using an ANOVA with treatment as

the factor. *P* values and 95% confidence intervals will be calculated based on pairwise contrasts within the ANOVA.

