11.5.1 ECG Mean Changes

Analyses of mean change from baseline to each double-blind visit value and to the minimum, maximum and final double-blind value will be presented for each ECG variable. Analyses of mean change from final double-blind value to final post-treatment value will also be presented for each ECG variable.

For each mean change analysis, the mean and median change will be presented for each treatment group. The mean change for each ABBV-8E12 dose group will also be compared to the mean change for the placebo group using an ANOVA with treatment as the factor. *P* values and 95% confidence intervals will be calculated based on pairwise contrasts within the ANOVA.

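### Continuous safety variables are compared on change from baseline without adjusting for baseline: valid, but less precise than ANCOVA on the same data

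*SAP*

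**What the plan says.** Four SAP sections share one model. In 11.3.1 (laboratory) the mean change in each dose group is "compared to the mean change for the placebo group using an ANOVA with treatment as the factor", and "95% confidence intervals will be calculated based on pairwise contrasts within the ANOVA". In 11.4.1 (vital signs and weight) it is again "compared to the mean change for the placebo group using an ANOVA with treatment as" the factor. In 11.5.1 the ECG comparison is made "using an ANOVA with treatment as the factor", and 11.6.2 (CSF safety variables) does the same. No baseline covariate is named in any of them, and the general rules in 11.1 do not add one. Those rules set the test: "Treatment group differences in safety parameters are evaluated using two-sided test at the significance level of 0.050".

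The protocol agrees. Section 8.1.6 says that differences in continuous safety variables "will be assessed using an ANOVA model with treatment as the main effect", unless otherwise specified. Sections 8.1.6.2 to 8.1.6.4 name one-way ANOVA for laboratory tests, vital signs and weight, and ECG.

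The baseline value is available for every subject who has a change score. SAP 6.2 says that baseline "shall refer to the last non-missing observation prior to the first dose of study drug".

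Elsewhere the SAP does adjust for baseline: in the primary MMRM (10.2), the subgroup ANCOVA (10.7) and the tau biomarker ANCOVA (13.0).

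**The concern.** A change score is usually negatively correlated with its own baseline: subjects who start high by chance tend to fall, and those who start low tend to rise. An ANOVA on change leaves that predictable part in the residual. The between-arm interval is then wider than it need be, although the covariate that would narrow it is already in the data set.

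Long-term safety is one of the two primary objectives. For laboratory, vital-sign and ECG variables, the SAP's shift tables and summaries of potentially clinically significant values (11.3.2, 11.3.3, 11.4.2, 11.5.2) exclude between-group comparisons. The ANOVA contrasts are therefore the only formal between-arm comparisons of these variables, and their width decides how small a drift can be seen or ruled out.

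**Working it through.** **The plan's own figures.** The documents state no precision target, SD or correlation for any safety variable, so there is no safety figure to reproduce. The only stated precision is the power of about 90% for the PSPRS comparison (SAP 4.3). It reproduces for the high dose: 110 per arm less 25% without data is 82.5; 0.56 × √(82.5/2) = 3.597; 3.597 − 2.241 (two-sided 2.5%) = 1.355; power 0.912. It confirms the arm size and nothing below depends on it.

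**Direction.** Let s0 and s1 be the baseline and follow-up SDs and r their correlation.

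- ANOVA on change, residual variance: s0² + s1² − 2·r·s0·s1
- ANCOVA, residual variance: s1²·(1 − r²)
- Difference: (s0 − r·s1)², which is never negative

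In large samples ANCOVA cannot be less precise. The two are equal only when r·s1 = s0, that is, when the slope of follow-up on baseline is 1.

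**Size with equal SDs (assumption).** The standard-error ratio ANCOVA/ANOVA is √[(1 − r²) / (2(1 − r))] = √[(1 + r)/2]. The half-widths below are 95% half-widths in SD units, from simulated three-arm data with 110 per arm, t intervals and the lost degree of freedom included.

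| r (assumed) | SE ratio | ANCOVA SE smaller by | ANOVA interval wider by | Half-width, ANOVA vs ANCOVA |
|---|---|---|---|---|
| 0.3 | √0.65 = 0.806 | 19% | 24% | 0.313 vs 0.253 |
| 0.5 | √0.75 = 0.866 | 13% | 15.5% | 0.265 vs 0.230 |
| 0.7 | √0.85 = 0.922 | 8% | 8.5% | 0.205 vs 0.190 |
| 0.9 | √0.95 = 0.975 | 2.5% | 2.6% | 0.119 vs 0.116 |

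**Unequal SDs.** Equal SDs are least plausible for change to the minimum or maximum value. If the follow-up SD is 1.2 times the baseline SD, the ratio is 0.873, 0.933, 0.983 and 0.989 at the same four correlations. It reaches exactly 1 in between, at r = 1/1.2 = 0.83. The direction holds, but the gain can be negligible.

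**Week 14 CSF subset.** SAP 11.6.2 limits this analysis to Cohort 1, which is 30 subjects, or about 10 per arm if 1:1:1 holds within the cohort (assumption). Simulated width ratios ANCOVA/ANOVA are 0.818 at r = 0.3, 0.882 at 0.5, 0.941 at 0.7, 0.996 at 0.9 and 1.007 at 0.95. Near 0.9 the gain is gone, and above that the lost degree of freedom slightly outweighs it.

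**Which changes the argument covers.** Sections 11.3.1, 11.4.1 and 11.5.1 apply the same ANOVA sentence to two kinds of change: from baseline to on-treatment values, and from the final double-blind value to post-treatment values. The algebra concerns a change and its own starting value. For the second kind that starting value is measured after randomization and may be affected by treatment, so it is not suitable as a baseline covariate. Section 11.6.2 contains only changes from baseline.

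**The case against.** The strongest reply is that nothing here is wrong. Treatment-only ANOVA on change is unbiased under randomization, its standard error already reflects chance baseline imbalance, and protocol and SAP agree on it. That stands. A reader might infer that the planned comparisons are biased, that their type I error is inflated, or that the primary efficacy result is touched; the documents support none of these.

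The second reply is that the size is unknown. That also stands. A reader might take the r = 0.5 case, where 1/0.75 = 1.33 corresponds to a third more subjects, as the loss in this trial. The documents give no correlation for any of these variables and set no precision target for safety, so that figure is one point on an assumed range, and at r = 0.9 the intervals differ by under 3%.

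Third, these tests are many 0.050-level screens over parameters, visits and two doses. Safety signals will also come from adverse-event summaries, shift tables, summaries of potentially clinically significant values and MRI evaluations. This is fair, and it limits the stakes. It does not remove the point, because those laboratory, vital-sign and ECG tables make no between-group comparison.

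Last, putting ANCOVA in place of ANOVA throughout these sections would also change the post-treatment analyses, where it does not belong, and would depart from the protocol. Both are correct, and the fix is limited accordingly.

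**Conclusion.** The point holds as a matter of precision. For change from baseline in laboratory, vital-sign and weight, ECG and CSF safety variables, the planned ANOVA is valid but in large samples never more precise than ANCOVA on baseline, and usually less. With equal SDs and an assumed correlation between 0.3 and 0.9, the ANCOVA standard error would be about 19% to 2.5% smaller. The gain shrinks to nothing when the slope of follow-up on baseline is near 1, and there is little or none in the Week 14 CSF subset at correlations of about 0.9 or more. The direction rests on algebra and the size on assumption. It is a desirable refinement that affects neither the validity of the safety comparisons nor the primary efficacy analysis.

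**What to change.** In SAP 11.3.1, 11.4.1, 11.5.1 and 11.6.2, for the change-from-baseline analyses only, specify ANCOVA with treatment as the factor and the baseline value of the variable as a covariate, with P values and intervals from pairwise contrasts in that model. State that changes from the final double-blind value to post-treatment values keep the treatment-only ANOVA.

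Protocol 8.1.6 and 8.1.6.2 to 8.1.6.4 name the ANOVA, so list the change in SAP Section 14, which already records departures from the protocol. The treatment-only ANOVA can be kept as a supportive analysis if continuity with the protocol is wanted.

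The cost is SAP wording, one entry in Section 14 and one extra model term in the programs. No new data are needed.
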